As noted above, the chief risk of TMS studies is seizure, yet this risk is significantly mitigated by well established, consensus guidelines with a proven track record for safe administration (Rossi et al. 2009; Rossi et al. 2020). Key methods for minimizing seizure risk include screening against risk factors among otherwise healthy young adult participants (e.g. epilepsy, history of brain trauma, the use of anti-depressants, etc.). Additionally, we will adhere closely to safety consensus guidelines as articulated by Rossi et al., which have a proven track record of safe administration. Nevertheless, as we cannot rule out seizure risk entirely, every experiment will be run by the PI ([name]) and a second experimenter trained to respond quickly and effectively in the event of a seizure. All experimenters will be thoroughly trained, and closely familiar with the protocol for responding including securing the participant to preclude further harm, contacting emergency medical services, remaining with and reassuring the participant until emergency medical services arrive, and subsequently documenting and reporting the incident to our IRB.

For MRI, there are no known risks beyond interactions between metal and the magnetic field. Hence, all participants are extensively screened for implanted metal. Persons at primary or secondary risk based on an implanted object or medical device will be excluded according to MRF operating procedures. Moreover, no personnel are permitted in the scanner room with any metal on their person. As such, we do not anticipate any significant risk from the application of these procedures. In rare cases, a participant will become anxious because of lying in an enclosed space. We will exclude participants who report a history of anxiety in enclosed spaces, and we will terminate the session of a participant who expresses anxiety about lying in the bore.

All participants will be able to stop the session at any time by squeezing a ball held in one hand. The ball activates a buzzer in the control room. There is also an intercom voice link with the control room that allows verbal communication between participant and experimenters.

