4 STUDY DESIGN

4.1 OVERALL DESIGN

The hypothesis to be studied in this Trial is that criticality in the brain depends on the balance of cortical excitation to inhibition and that sub-criticality impacts on working memory and subjective cognitive effort. This hypothesis leads to predictions including that TMS protocols which decrease the cortical excitation to inhibition ratio (like theta burst stimulation) will make the brain more sub-critical. In turn, when theta-burst stimulation is targeted at regions involved in working memory like the dorsolateral prefrontal cortex, this predicts worse, more inflexible working memory performance and greater subjective effort when people are engaged in working memory tasks.

We will use a repeated measures design wherein every subject is their own control. Specifically, on different days, separated by at least one week, participants will receive continuous theta burst stimulation to either their dorsolateral prefrontal cortex (the active condition) or the angular gyrus (the control condition). The order of these sessions is pseudo-randomized across participants. Specifically, 15 of our target 30 participants will be randomly pre-assigned to complete an active condition session first and control condition second and vice versa for the other 15 participants. The pre-assignment will be determined by permutation of a list of subject numbers before recruitment starts. Every subject number will subsequently be assigned to participants in order of their recruitment. Errors in randomization will be documented and session order will be included as a covariate in all analyses.

Participants will come in for three sessions: 1) a first session to complete paperwork and an MRI structural scan for subsequent neuronavigation and a resting state scan, 2) one counterbalanced order session for dorsolateral prefrontal cortex stimulation and working memory task performance and 3) another counterbalanced order session for angular gyrus stimulation and working memory task performance. The first stimulation session can happen the day after an MR scan (but no more than 113 days after the MR

scan) and the second stimulation session can happen one week after the first stimulation session (but no more than 113 days after the first stimulation session).

This is a single-site trial.

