6.2 FIDELITY

6.2.1 INTERVENTIONIST TRAINING AND TRACKING

All TMS operators will receive training on the two key variables which may affect the consistency of cTBS. The first is the strength of stimulation intensity. Here, stimulation intensity will be based on participants' active motor threshold, which is diagnosed with the use of TMS-evoked potentials measured by electromyography and leads attached to participants' right hand, pursuant to a single pulse to their motor cortex hand knob. Motor thresholding will be based on a semi-automated threshold detection algorithm which is given feedback about the efficacy a given pulse for eliciting a motor evoked potential of 100 microvolts from peak to trough. Thus threshold identification should be standardized across participants, as should corresponding stimulation intensities.

The second degree of freedom is the precision of TMS targeting. For both motor threshold detection and cTBS, it is important to ensure precise targeting (of the hand knob and dlPFC, respectively). To ensure consistent targeting, we will use participant-specific structural MRI scans coupled with 3D vision-based neuronavigation systems. The neuronavigation system gives real-time feedback for precision targeting. Also, the exact location of every single pulse is recorded during stimulation, to ensure consistency. Finally, only two TMS operators will be used for the entirety of the study (the PI and one assistant), and both will be thoroughly trained to ensure consistent administration.

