6.3 MEASURES TO MINIMIZE BIAS: RANDOMIZATION AND BLINDING

All participants will complete both one target and one control stimulation session, but the order of these sessions will be pseudo-randomized. Specifically, participants will be assigned participant ID numbers based on their order of recruitment, but the participant ID numbers will be pseudo-randomized with respect to the order of target versus control stimulation sessions. Pseudo-randomization of IDs will be saved in a digital file and included in all subsequent analyses as a covariate of no interest. Any breaking of pseudo-randomization will be corrected with subsequent re-pseudo-randomization of unassigned ID numbers to ensure balance in session orders across participants. This pseudo-randomization will be managed / maintained by the PI.

The specific session that a participant is in (target versus control region) will be known to the experimenter (there is no way for the experimenter not to know since they are administering stimulation). To mitigate the impact on participants, they will be instructed that we will stimulate the brain on two different days, making no reference to possible differential effects across brain regions. The experimental condition will not be explained to the participant until the end of their participation, during debriefing.

Any instance of accidental unblinding – e.g. the participant learns that dlPFC stimulation is considered target, and angular gyrus is considered control stimulation will be noted and subsequent analysis will be conducted both including and excluding these participants to ensure that their inclusion has no effect on the conclusions of the study.

While it may be possible for some participants to infer that effects of stimulation at different sites should have differential effects, they will not be made aware which sites we expect to impact on working memory performance or subjective effort.

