7.2 PARTICIPANT DISCONTINUATION/WITHDRAWAL FROM THE STUDY

Participants are free to withdraw from participation in the study at any time upon request.

An investigator may discontinue a participant from the study for the following reasons:

- Identification of brain abnormalities during the MRI scan
- Non-compliance with regards to cognitive task instructions
- Lost-to-follow up; unable to contact subject (see **Section 7.3, Lost to Follow-Up**)
- Any event or medical condition or situation occurs such that continued collection of follow-up study data would not be in the best interest of the participant or might require an additional treatment that would confound the interpretation of the study; With TMS an unlikely but possible medical condition would be onset of a seizure
- The participant meets an exclusion criterion (either newly developed or not previously recognized) that precludes further study participation

The reason for participant discontinuation or withdrawal from the study will be recorded on the Case Report Form (CRF). Subjects who sign the informed consent form and are randomized but do not receive the study intervention may be replaced. Subjects who sign the informed consent form, and are randomized and receive the study intervention, and subsequently withdraw, or are discontinued from the study, will be replaced.

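### Session orders are tied to recruitment number and kept by the PI, who also runs the sessions, so each order is known before eligibility is settled; the bias risk is small and cheap to reduce

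*Protocol*

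**What the plan says.** Section 4.1 sets up two sequences: "15 of our target 30 participants will be randomly pre-assigned to complete an active condition session first and control condition second", with the reverse order for the other 15. On how the list is made it says "The pre-assignment will be determined by permutation of a list of subject numbers before recruitment starts", and on how it reaches people, "Every subject number will subsequently be assigned to participants in order of their recruitment". Section 6.3 repeats the link to recruitment order, stores the list in a digital file, and allows unassigned ID numbers to be re-randomized to restore balance if the sequence is broken. It then says: "This pseudo-randomization will be managed / maintained by the PI".

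Section 2.3.3 says that "every experiment will be run by the PI" together with a second experimenter. Section 6.2.1 limits the TMS operators to the PI and one assistant. Section 6.3 accepts that the experimenter knows the site, because that person delivers the stimulation.

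On departures, Section 7.2 says "Subjects who sign the informed consent form and are randomized but do not receive the study intervention may be replaced", and that people who leave after stimulation will be replaced. Task non-compliance is among the reasons for which an investigator may discontinue someone. The section does not say which order a replacement takes.

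The safeguards stated are that every participant receives both conditions, that session order is a covariate, and that randomization errors are documented.

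**The concern.** The next recruit gets the next number, and each number already carries an order. Whoever holds the list therefore knows a person's order before that person consents, completes the screening forms or has the MRI. No section names an independent holder, a sealed or scripted release, or any point before which the order is hidden. The reason given for the unblinded experimenter covers the stimulation visit. It does not explain why the order should be known while eligibility is still open, or why an operator should redraw the remaining numbers.

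At stake is the comparability of the two sequence groups. Section 3 states that accuracy and speed improve across sessions and that tasks come to feel less effortful. If the groups differed in how much they change from one session to the next, that difference would be read as a stimulation effect on N-back or effort.

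**Working it through.** **The plan's own figure, to settle the test convention.** Section 9.2 gives 80% power for 30 participants at d = 0.53 and p < 0.05. A paired t-test with n = 30 gives 80.1% two-sided and 88.3% one-sided, so the figure reproduces as two-sided. Two-sided 0.05 is used below. The point does not otherwise rest on this figure.

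**How predictable the order is.**
- With the list in hand, 30 of 30 orders are known.
- Suppose instead that the list is concealed, and an operator remembers past orders and always guesses the one with more places left. With m = 15 per sequence, the expected number of correct guesses is m + (4^m / C(2m, m) − 1)/2. Here 4^15 = 1,073,741,824 and C(30, 15) = 155,117,520, with ratio 6.922. The result is 15 + 5.922/2 = 17.96 of 30, about 60%. A simulation of 100,000 lists gave the same answer.

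**What can bias the contrast.** Let τ be the true dlPFC-minus-angular-gyrus effect. Let g_A be the mean practice gain (second session minus first) in the dlPFC-first group, and g_B the gain in the other group. First session minus second has expectation:
- dlPFC first: τ − g_A
- angular gyrus first: −τ − g_B

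Half the difference between the groups is τ − (g_A − g_B)/2. Three things follow.
- Stable differences in level drop out. A simulation with groups 0.8 SD apart in level gave a bias of 0.00 and a rejection rate of 4.9%.
- A practice gain common to both groups (g_A = g_B) drops out.
- A gap between the gains enters at half its size. In a two-sequence, two-session design the condition effect is itself the sequence-by-session interaction. A covariate for session or for sequence therefore cannot absorb a gain that differs by sequence.

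**Size under assumed gaps.** The protocol gives no variance or practice-effect figure, so the gaps are assumptions, in SDs of the within-person session difference. With 15 per sequence, the standard error of the contrast is √(1/15 + 1/15)/2 = 0.183. Rejection rates come from the noncentral t with 28 df and no true effect.

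| Assumed gap (SD) | Bias (SD) | Rejection rate |
|---|---|---|
| 0 | 0 | 5% |
| 0.2 | 0.10 | 8.3% |
| 0.3 | 0.15 | 12.5% |
| 0.5 | 0.25 | 26.2% |

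**Which gaps are credible before stimulation.** In the schedule (Section 1.3), the working memory, effort and EEG outcomes are first recorded at Visit 2. Visit 1 has consent, demographics, history, compatibility checks, height and weight, and scans. Selection at that stage could act only through a proxy. If a visible trait correlated 0.2 with practice gain (an assumption), a 0.2 SD gap in gain would need the groups to differ by 0.2/0.2 = 1 SD on the trait. A 0.5 SD gap would need 0.5/0.2 = 2.5 SD.

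**Which outcomes are exposed.** The functional E/I and criticality predictions in Section 9.1 compare rest before stimulation with recordings after it, within a session. A practice-gain gap between sequences does not enter them. The exposed contrasts are the between-session ones for N-back and effort.

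**The case against.** The strongest objection is that the order is known when there is almost nothing to select on. No one has seen task performance before the first stimulation visit, still less change between two sessions. Candidates declare for themselves whether they meet the criteria (Section 5.5), and a phone check follows (Section 8.1). Everyone receives both conditions. This stands, and it is why the risk is small.

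Several stronger readings are tempting and fail on the text.
- A reader might take the Section 7.2 wording that such people may be replaced as a power to drop an unwanted participant. It concerns filling a vacancy; the grounds for discontinuation are listed separately, and none mentions session order.
- Rescreening in Section 5.4 might look like a route to selection. Its examples have the same person returning after rest or without hair products, which moves a date and does not change who is in a sequence.
- A reader might infer that the PI controls recruitment and replacement. Sections 5.5, 7.2 and 7.3 refer to the team, an investigator or a designee. PI involvement is plausible but not stated.
- The 26% rate might be quoted as the likely damage. For selection before stimulation it would need an implausible imbalance on a proxy.

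The objection also notes, rightly, that concealment misses the likelier opening: discontinuation for task non-compliance after the first stimulation session, followed by mandatory replacement. By then the operator must know the site. This does not defend the present arrangement, but it means that concealment alone is not enough.

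**Conclusion.** The point holds in a limited form. The protocol fixes an arrangement in which each order is known before consent and eligibility are settled, to a person who also runs the sessions and may redraw unassigned numbers, and it gives no reason that covers that period. It shows an opportunity for selection; nothing in it shows that selection occurs or is intended, and the gap in practice gain may be zero.

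The exposure is the between-session N-back and effort contrasts, at half of any between-sequence gap in session-to-session change. An assumed gap of 0.2 SD gives a bias of 0.10 SD and an error rate of about 8% instead of 5%, with 15 per sequence and a two-sided test. This is a smaller problem than missing concealment in a parallel-group trial, and a cheap improvement rather than a defect that undermines the study.

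**What to change.** Amend Sections 4.1, 6.3 and 7.2 as follows.
1. Keep the 15/15 permutation, but hold it in a locked script or database on the existing server, or with an existing lab member who does not recruit, screen or operate TMS.
2. Release one order at a time, with a time stamp, only after consent, screening forms and MRI are complete and eligibility is logged.
3. Have any redraw of unassigned IDs done by that script or holder, not by the PI.
4. State that a replacement takes the vacated order.
5. Report all randomized participants by sequence, including those discontinued or replaced, with reasons.

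This needs no extra participants, visits or procedures. The cost is that both neuronavigation targets must be prepared before the first stimulation visit. Two limits remain. An unblinded operator who remembers past orders can still guess about 18 of 30, and a replacement's order can be foreseen by anyone who knew the vacated one. Concealment also does not reach discontinuation after the first stimulation session; item 4 preserves the balance of the sequences there, and item 5 makes such departures visible.

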9 STATISTICAL CONSIDERATIONS

There will not be a formal Statistical Analysis Plan (SAP). Also, no statistical plan will be posted publicly or registered before the study begins.

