9.4.2 ANALYSIS OF THE PRIMARY ENDPOINT(S)

The following key outcomes will be assessed in this study. All measures are interval with the exception of the categorical covariate of sex.

- Subjective effort
 - Likert scale ratings (ranging from 1-10) of task-induced effort, demand, time pressure, and stress
 - subjective values as estimated from an indifference point discounting procedure
 - self-reported motivation to engage in demanding tasks on a set of Likert scales with continuous values ranging from 0-20
- E/I balance
 - fEI derived measure with exponents ranging approximately from 0.0-2.0
 - power-law exponents with exponents approximating -2.0
- Critical dynamics
 - Long range temporal correlations – a derived measure with exponents ranging approximately from 0.5-1.0
 - Avalanche size and duration distribution exponents approximating -2.0 and -1.5, respectively
- N-back working memory performance
 - overall accuracy rate as a percentage
 - median correct reaction times by trial type: lures versus targets versus regular trials
 - the discrimination index d'

Primary analyses of these outcomes will entail multiple regression models in which outcomes will be regressed on cTBS condition (target versus sham), controlling for sex and age.

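### Masking in section 6.3 covers participants only: nothing keeps knowledge of condition out of offline EEG processing, although that step could be masked at low cost

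*Protocol*

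**What the plan says.** **Who knows the condition.** Section 6.3 states that the site "will be known to the experimenter (there is no way for the experimenter not to know since they are administering stimulation"). Section 6.2.1 adds that "only two TMS operators will be used for the entirety of the study (the PI and one assistant"). On the order list, 6.3 says "This pseudo-randomization will be managed / maintained by the PI".

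**Who is masked.** Participants receive neutral instructions, and "The experimental condition will not be explained to the participant until the end of their participation, during debriefing". If a participant is accidentally unblinded, the analysis is run with and without that participant. Section 6.3 describes no masking of anyone else.

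**What fixes the analysis.** Section 9 opens with "There will not be a formal Statistical Analysis Plan (SAP). Also, no statistical plan will be posted publicly or registered before the study begins".

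**What the EEG endpoints are.** Section 9.4.2 describes the temporal-correlation measure as "a derived measure with exponents ranging approximately from 0.5-1.0" and lists "Avalanche size and duration distribution exponents approximating -2.0 and -1.5, respectively". Section 9.1 locates the expected effects only as close to the stimulated targets, and the section 3 table refers to channels near the site. Section 8.1 specifies a 64-channel system that records throughout each stimulation session.

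**The concern.** Long-range temporal correlation exponents, avalanche exponents and functional E/I are not read directly off the amplifier. Each is computed after decisions such as which stretches of signal to reject, which channels count as near the target, what range to fit and what threshold defines an avalanche. The protocol does not list these decisions; the need for them is inferred from the nature of the measures.

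Section 9.1 predicts a direction (reductions), so the favourable outcome is known in advance. If a person who knows a segment's condition makes these decisions segment by segment, they can be shaded toward that outcome without intent. At stake are the criticality endpoints, which are primary in sections 1.1 and 3. Functional E/I is also exposed: it is secondary in those sections but appears among the primary hypotheses in 9.1 and the key outcomes in 9.4.2.

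**Working it through.** The protocol gives no figure on this point, so the check is mainly a comparison of its statements.

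**Step 1. What the stated reason covers.** The justification in 6.3 is that the operator must know where the coil goes. That is true while stimulation is delivered. Processing happens later on stored recordings, and nothing about it requires the site or the time point to be visible, provided channel sets are fixed in advance.

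**Step 2. Whether anything separates the roles.** Section 6.2.1 makes the PI an operator, and 6.3 makes the PI keeper of the order list. No section says who processes the EEG, and none plans coded recordings, a masked processor or a masked analyst.

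**Step 3. Whether the decisions are fixed elsewhere.** Section 9 excludes a formal SAP and any posted or registered plan. Section 9.4 does fix the list of measures, a regression on condition with sex and age, and p < 0.05 with correction for multiple comparisons. None of this constrains artifact rejection, channel choice, fitting range or threshold.

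**Step 4. Which labels matter.** Two contrasts are planned for the EEG measures:

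| Contrast | Where | Label that could bias processing |
|---|---|---|
| Post versus pre-stimulation, near the stimulated site | 9.1; t-tests in 9.4.1 | pre/post |
| Target versus control site | regression in 9.4.2 | site |

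Coding the session alone would protect only the second row. Rest segments need their pre/post status hidden as well.

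**Step 5. What a given bias would do (illustration).** Take a paired t-test, n = 30, two-sided 0.05, no true effect, and suppose processing shifts the mean paired difference by b standard deviations. The false-positive rate is P(|T| > 2.045), where T is noncentral t with 29 degrees of freedom and noncentrality b × √30.

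- b = 0: noncentrality 0, rate 5%
- b = 0.1: noncentrality 0.55, rate 8.3%
- b = 0.2: noncentrality 1.10, rate 18.5%
- b = 0.3: noncentrality 1.64, rate 35.5%

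The values of b are assumptions. Nothing in the protocol indicates which applies, or that b differs from zero.

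**Step 6. A separate problem: an unfixed pipeline (illustration).** Simulate null trials with n = 30 and keep the smallest two-sided p-value among k processing variants whose results correlate at r.

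| r | k = 2 | k = 3 | k = 5 |
|---|---|---|---|
| 0.8 | about 8% | about 10% | about 13% |
| 0.6 | about 9% | about 12% | about 17% |

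If only results in the predicted direction count, the starting rate is 2.5%. It rises to about 4%, 5% and 6% at r = 0.8, and to about 4%, 6% and 8% at r = 0.6. Both k and r are assumptions. These figures describe choosing among pipelines after seeing test results. They do not estimate the effect of missing masking, and a pipeline fixed in advance would remove this inflation without any masking.

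**The case against.** **Other bias controls exist.** A reader might infer that nothing beyond participant masking protects the trial. The protocol does not support that. Session order is permuted before recruitment and used as a covariate (4.1), motor thresholding is semi-automated, and neuronavigation records every pulse (6.2.1). These are real controls on allocation and delivery. None reaches the EEG processing step, so the narrower point stands.

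**The protocol does not say that the operators process the EEG.** This is correct. It leaves the possibility open and does not state it as a plan. The finding is the absence of a separation, not evidence of misuse.

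**Such detail usually belongs in a SAP.** Normally it would, but section 9 says that no formal SAP will be written, so this reply does not answer the point.

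**Multiplicity correction is planned.** Section 9.4.1 promises it. It applies to the tests that are run and counted, not to processing variants that are discarded.

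**Masking is not free or automatic.** This stands. EEG runs throughout the session, so stimulation artifact could reveal the site, and choosing channels by site would reveal it too. Both have to be handled before coding works.

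**This is a small mechanistic study in healthy volunteers.** That limits the consequences. It does not weaken the case for a cheap safeguard on the primary EEG endpoints.

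**Conclusion.** The point holds as a gap in masking at the processing stage. Section 6.3 masks participants only, its reason for not masking the experimenter stops at delivery, and no other section keeps condition hidden while the EEG measures are derived. It is a worthwhile, inexpensive improvement to make before processing begins, not a flaw that invalidates the design.

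Its size is unknown. A reader might take the 8% to 17% range in the working as the error rate caused by missing masking. It is not: those figures concern selection among unfixed pipelines under an assumed number of variants and an assumed correlation. The shift calculation shows how sensitive a 30-participant paired test is to a modest bias, but the bias itself is assumed.

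The conclusion rests on one inference, that these derived EEG measures require processing decisions, and on the protocol's own statement that no SAP will fix them.

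**What to change.** Add a paragraph to section 6.3 stating that:

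1. Rest and task EEG segments are cut out of the recordings, leaving out the stimulation periods.
2. A script gives each segment a random code that hides the stimulated site and, for rest segments, whether it is pre- or post-stimulation. The code file stays closed to whoever processes the data.
3. One processing pipeline and the channel sets for both sites are fixed beforehand, and both sets are computed for every segment regardless of site.
4. Codes are broken only after artifact rejection, fitting and the derived measures are complete and locked.

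Item 3 also removes the separate problem of choosing among pipelines by result. The cost is a short script, one paragraph and a small delay before condition-level results can be seen. Sample size, visits and stimulation procedures do not change.
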